Protocol Version No.: 14

COH Protocol No.: 16403

Agent: Nivolumab, Ifosfamide, Carboplatin, Etoposide

Sponsor/IND#: City of Hope/133829

NCT number NCT03016871

Participating Sites City of Hope, MD Anderson Cancer Center, Yale Cancer Center, Dana-Farber Cancer Institute

Principal Investigator

[name]
City of Hope National Medical
Center
Hematologic Malignancies and
Stem Cell Transplantation Institute
[name]
[name]
O: [contact] [name]
Email: [contact]

Data Coordinating Center

City of Hope National Medical
Center
[name]
[name]
Email: [contact]

Protocol Team

Biostatistician/Co-Investigator

[name]

Department of Quantitative and Computational Medicine
City of Hope National Medical Center
[name]
[name]
O: [contact]
Email: [contact]

Co-Investigator

[name]

Department of Diagnostic Radiology
City of Hope National Medical Center
[name]
[name]
O : [contact]
Email : [contact]

Participating Non-COH Sites

Co-Investigator

[name] [name]

MD Anderson Cancer Center
Department of Lymphoma/Myeloma
[name]
[name]
O: [contact]
F: [contact]
Email: [contact]

Co-Investigator

[name]

Yale Cancer Center
[name]
[name]
O: [contact]
Email: [contact]

Translational Investigator

[name]

Dana-Farber Cancer Institute
Division of Hematologic Neoplasia
[name]
[name]
O: [contact]
F: [contact]
Email: [contact]

[figure not shown]
Translational Investigator

[name], PhD

Dana-Farber Cancer Institute
Department of Pathology
[name]
[name]
O: [contact]
Email: [contact]

Experimental Design Schema

Original Design Schema (Cohort A)

Note: Nivolumab dosing is 240 mg IV every 2 weeks for the first 12 weeks or 6 cycles.

When in combination with ICE, the dosing is 240 mg IV every 3 weeks for 6 weeks or 2 cycles.

ICE:Ifosfamide: 5000 mg/m² continuously on D2, IV

Carboplatin: AUC 5 on D2, IV

[figure not shown]
Etoposide: 100 mg/m² D1-3, IV

Mesna: 5000 mg/m² continuously on D2, IV

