†Tumor biopsy (if safe and accessible) must be performed after the first CT/PET response assessment (and only in patients who did not reach CR). For patients (with PR) who are going to a second 6-week treatment with single-agent NIVO, biopsy may be performed at any time after the first CT/PET scan (but before any NIVO+ICE treatment). For patients (with SD or PD at first CT/PET) who are instead going to a 6-week treatment with NIVO+ICE, biopsy must be performed before starting NIVO+ICE.

*Patients who only achieve SD after 6 weeks of single agent nivolumab can either receive an additional 6 weeks of single agent nivolumab, or receive a combination of nivolumab plus ICE for 6 weeks. The decision to go either way will be at the physician/investigator's discretion on a case-by-case basis.

New Cohort Design Schema (Cohort B)

To enroll after completion of Cohort A.

Note: Nivolumab dosing is 240 mg IV on the first week of the initial 14 day cycle. In combination with ICE, nivolumab dosing is 240 mg IV every 3 weeks for 2-3 cycles. ICE is as indicated in [Section 5.1.2](#).

†Tumor biopsy (if safe and accessible) must be performed before starting NIVO+ICE.

‡ Patients achieving PR may proceed to AHCT at the physician/investigator's discretion on a case-by-case basis

Protocol Synopsis

| | |
|---|---|
| Protocol Title: | |
| A phase II trial of response-adapted second-line therapy for Hodgkin lymphoma using anti-PD-1 antibody nivolumab ± ICE chemotherapy as a bridge to autologous hematopoietic cell transplant (NICE Trial) | |
| Brief Protocol Title (Lay Public): | |
| A phase II study of nivolumab with or without ICE for high-risk Hodgkin lymphoma | |
| Study Detail | |
| Indication(s): | Hodgkin lymphoma |
| Phase: | II / Single Arm |
| Number of Participants: | Original Cohort (A): 43; New Cohort (B): 35 |
| Expected Accrual Duration: | 24 months (1-2 subjects/month): New Cohort (B) 24 months |
| Estimated Study Duration: | 72 months |
| Anticipated Participant Duration: | 24 months: |
| Participating Sites: | 
 • City of Hope; Duarte, CA • MD Anderson Cancer Center; Houston, TX • Yale Cancer Center, New Haven, CT • Dana Farber Cancer Institute, Boston, MA |
| Study Agents: | 
 • Nivolumab (anti-PD-1 monoclonal antibody) • Ifosfamide • Carboplatin • Etoposide |
| Sponsor: | City of Hope National Medical Center |
| Industry Partner: | Bristol-Myers Squibb (BMS) |
| Study Rationale: | |

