Because a number of patients are expected to be given ICE salvage therapy in combination with nivolumab, it will not be possible in these patients to isolate the treatment effect of nivolumab. Our clinical endpoint, however, is complete response rate at the time of transplantation. Our design is to assess 1) the toxicity of nivolumab + ICE chemotherapy and 2) the sequential approach of nivolumab alone, potentially followed by nivolumab + ICE, and the effect of this strategy on the CR rate at the time of transplant.

This study will be conducted in compliance with the protocol, Good Clinical Practice (GCP), and the applicable regulatory requirements.

2.5 Rationale for New Cohort (Cohort B).

With enrollment on the original design almost completed (Cohort A), we have found that 22 out of 28 patients responded to NIVO and have proceeded to AHCT without receiving the combination of NIVO+ICE. Thus we have not completely assessed the safety of NIVO+ICE, nor have we obtained a preliminary estimate of the anti-lymphoma activity of the combination, which was the primary objective for Cohort A. We therefore are unable to fully characterize the NIVO+ICE combination using the original trial design. An additional consequence of a large majority of patients achieving a complete response with

nivolumab alone and proceeding directly from NIVO to AHCT is that very few on-treatment biopsies have been obtained for the correlative studies that were designed to address the exploratory objectives. We propose to include a cohort of high-risk patients with relapsed or refractory HL after frontline therapy to receive a single dose of NIVO prior to NIVO+ICE combination. We have restricted this cohort to only include high-risk patients (e.g. primary refractory HL, extranodal disease at relapse) since these patients have the highest risk of treatment failure using salvage therapy and autologous stem cell transplantation and thus justify the use of combination therapy rather than a PET-adapted approach. In addition, patients who have received brentuximab vedotin as part of frontline therapy will be eligible since identification of a novel salvage regimen that does not contain brentuximab vedotin is an important unmet need in this population. On treatment biopsies will be obtained on all these patients after the single dose NIVO and prior to the first dose of NIVO+ICE.

Updated Apr 27, 2021

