9.1 Lymphoma specimen studies

9.1.1 Tissue collection timepoints

Each subject will have either a fresh core or excisional biopsy of a tumor lesion prior to starting study therapy or will have available archival tissue from a biopsy that was performed after induction therapy.

Patients who are not in CR by CT/PET scan at 6 weeks will undergo biopsy of lymphoma samples (if tumor is accessible, and the procedure is medically safe) to assess for biomarkers for lack of CR. Tumor biopsy (if safe and accessible) must be performed after the first CT/PET response assessment. For patients (with PR) who are going to a second 6-week treatment with single-agent NIVO, biopsy may be performed at any time after the first CT/PET scan (but before any NIVO+ICE treatment). For patients (with SD or PD at first CT/PET) who are instead going to a 6-week treatment with NIVO+ICE, biopsy must be performed before starting NIVO+ICE (**except** for patients on Cohort B, enrolled after approval of Version 14.0). If feasible, all subjects will also undergo biopsy of tumor lesion at the time of disease progression or relapse.

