- a) Immunohistochemistry ([name]) for expression of CD25, CD68, HLA class I and II molecules, PD-1, PD-L1, and PD-L2 in tumor samples (LN, BM). Expression of other receptors/checkpoint molecules may also be assessed. IHC for these markers will be performed on pre- and post-treatment biopsies and expression will be scored in deciles by a hematopathologist blinded to the clinical results. We will compare baseline to on-treatment expression levels.
- b) FISH of the 9p24.1 region will be performed as previously described⁷⁶ in the City of Hope Cytogenetics Core Laboratory on pre-treatment HL tumor samples and results will be defined as previously - disomy, polysomy, copy gain, amplification. The association between 9p24.1 alteration type and response to nivolumab/NIVO + ICE therapy will be evaluated.
- c) RNA sequencing of whole tumor samples (to include Hodgkin cells and immune/stromal cells in the tumor microenvironment) of pre-study treatment tumor samples to assess the potential relationship between genetic alterations of the tumor or tumor microenvironment and response. We will also evaluate GEP by RNA sequencing in on-treatment biopsies. With sophisticated de-convolution algorithms, we will identify and quantitate all the major immune cell populations based on the GEP data.
- d) Perform quantitative spatial image analysis ([name]) of immune and tumor cells in pre-study treatment, on-treatment, and post-progression tumor samples via 8-color histology using the Vectra system to assess the presence of and spatial relationships between tumor infiltrating lymphocytes/immune cell populations (e.g., CD8+ and regulatory T cells) and immune checkpoint ligand/receptors (i.e., PD-1 and PD-L1).
- e) Perform peripheral blood flow cytometry of immune cell subsets (including PD-L1 and PD-L2 bearing lymphocytes) (CISCL) at various time points of blood collection to determine the impact of study therapy on immune cell subsets during study therapy and immune reconstitution after AHCT. We will also perform T-cell receptor (TCR) repertoire analysis to assess the TCR repertoire diversity after study therapy.

- f) TCR repertoire analysis on the tumor sample will be performed via NGS to assess the TCR repertoire and diversity of tumor infiltrating lymphocytes.

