^f PET-CT scans will be performed at end of weeks 6, 12, and 18. Once PET-CT is negative, it does not need to be performed again. Instead, a diagnostic quality CT of the neck, chest, abdomen, and pelvis will be performed.

^g Each subject will have either a fresh core or excisional biopsy of a tumor lesion prior to starting study therapy or will have available archival tissue from a biopsy that was performed after induction therapy.

^h Tumor biopsy (if safe and accessible) must be performed after the first CT/PET response assessment (and only in patients who did not reach CR). For patients (with PR) who are going to a second 6-week treatment with single-agent NIVO, biopsy may be performed at any time after the first CT/PET scan (but before any NIVO+ICE treatment). For patients (with SD or PD at first CT/PET) who are instead going to a 6-week treatment with NIVO+ICE, biopsy must be performed before starting NIVO+ICE.

ⁱ If feasible, all subjects will undergo biopsy of tumor lesion at the time of disease progression or relapse.

^j On Day 1 of Wks 1, 3, 5 of nivolumab, on Day 1 of Wks 1 and 4 of NIVO + ICE, and on last day of Wk 6 (C2D21) of NIVO + ICE or any day post-C2D21, but must be prior to AHCT.

^k Tumor measurements will be performed at the same time points indicated for PET-CT scans in footnote f.

^l Includes all patients, regardless of reason for end of protocol therapy; refer to [Section 5.5](#) for follow-up.

^m For patients who receive AHCT

ⁿ Refer to [Section 5.5](#) for post-AHCT survival assessments.

*Serum chemistry includes comprehensive metabolic profile: sodium, potassium, chloride, carbon dioxide, glucose, blood urea nitrogen, creatinine, AST, ALT, Alkaline phosphate, total bilirubin, calcium, albumin, total protein, magnesium, phosphate

** Women of childbearing potential must have a negative serum or urine pregnancy test (minimum sensitivity 25 IU/L or equivalent units of HCG) within 24 hours prior to the start of nivolumab.

† Must be performed within 10 days of treatment initiation.

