10.2 Calendar of Events: New Design (Cohort B)

| Study Parameters and Calendar | Within 28 ^a days of D1 | Cycle 1 (14 days) | | Cycle 2+ (21 days) | | End of Treatment ¹ | Post AHCT f/u |
|--|-----------------------------------|-------------------|-----------------------|-----------------------|------------------------------------|-------------------------------|----------------|
| | | D1 (\pm 3 day) | C2, D1 (\pm 3 day) | C3, D1 (\pm 3 day) | C4, D1 ^m (\pm 3 day) | | |
| Nivolumab | | X | X | X | (X) | | |
| Ifosfamide ^c | | | X | X | (X) | | |
| Carboplatin ^d | | | X | X | (X) | | |
| Etoposide ^e | | | X | X | (X) | | |
| Informed consent | X | | | | | | |
| Demographics | X | | | | | | |
| Medical history | X | | | | | X | |
| Concurrent meds | X | X | X | X | (X) | X | |
| Physical exam | X | X | X | X | (X) | X | |
| Vital signs | X | X | X | X | (X) | X | |
| Height | X | | X | | | | |
| Weight | X | X | X | X | (X) | X | |
| Performance Status | X | X | X | X | (X) | X | |
| CBC w/diff, plts ^f | X | X | X | X | (X) | X | |
| Serum chemistry* [†] | X | X | X | X | (X) | X | |
| PT/PTT/INR [†] | X | X | X | X | (X) | X | |
| TSH, T3, T4 [†] | X | X | X | X | (X) | X | |
| EKG (as indicated) [†] | X | | | | | | |
| PFTs | X | | | | | | |
| Adverse event evaluation | | X | X | X | (X) | X | X ⁿ |
| Tumor measurements | X ^k | | | X ^k | | | |
| Radiologic evaluation ^f | X ^a | | | X ^f | (X) | | |
| Tumor Biopsy ^g | X | | | | | (X ⁱ) | |
| B-HCG [†] | X | X ^{**} | | | | | |
| Research blood collection ^j | | X ^j | X ^j | X ^j | | | |
| Survival | | | | | | | X ^o |

^a Except for screening PET/CT, which can occur within 35 days of D1.

^b Filgrastim 5 mcg/kg given on days 5 to 12

^c 5 g/m² with equivalent dose of Mesna given over 24 hours by continuous infusion on day 2 (inpatient schedule) or 1670 mg/m² with Mesna on Days 1-3 (outpatient schedule).

^darea under the curve (AUC) of 5 with a maximum of 750 mg day 2

^e 100 mg/m²/day on days 1 to 3

^f PET-CT scans will be performed at end of week 8. Once PET-CT is negative, it does not need to be performed again. Instead, a diagnostic quality CT of the neck, chest, abdomen, and pelvis will be performed.

^g Each subject will have either a fresh core or excisional biopsy of a tumor lesion prior to starting study therapy or will have available archival tissue from a biopsy that was performed after induction therapy.

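### Version 14 both calls for and waives an on-treatment tumour biopsy in newly enrolled Cohort B patients, and the Cohort B calendar and tissue form have no time point for one

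*Combined protocol and SAP*

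**What the plan says.** The document is labelled "Protocol Version No.: 14", so all of the following is current text.

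- **Section 2.5 (rationale for Cohort B):** "On treatment biopsies will be obtained on all these patients after the single dose NIVO and prior to the first dose of NIVO+ICE". No exception is attached. The dated April 2021 update starts directly below this sentence and leaves it as it is.
- **Cohort B design schema, footnote:** "Tumor biopsy (if safe and accessible) must be performed before starting NIVO+ICE". This is conditional on safety and access, but not on protocol version.
- **Section 9.1.1:** patients with stable or progressive disease at the first scan who go on to NIVO+ICE must be biopsied before the combination starts. A parenthesis then makes an exception "for patients on Cohort B, enrolled after approval of Version 14.0".
- **Section 10.2 (Cohort B calendar):** the biopsy row is marked at screening, with the footnote "Each subject will have either a fresh core or excisional biopsy of a tumor lesion prior to starting study therapy" (or archival tissue instead). The only other mark points to footnote i, which has the same wording in both calendars: "If feasible, all subjects will undergo biopsy of tumor lesion at the time of disease progression or relapse". The cells for Day 1 of Cycles 1 to 4 are empty, and the footnotes pass from g to i. The Cohort A calendar in Section 10.1 keeps a footnote h with an on-treatment biopsy for patients not in CR.
- **Section 9.1.3 and Appendix C:** the labelling text and the tissue form name only baseline and progression as time points.
- **Section 9.3:** for immunohistochemistry, "We will compare baseline to on-treatment expression levels". RNA sequencing and spatial imaging are also planned on on-treatment tissue.

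**The concern.** For a Cohort B patient enrolled after approval of Version 14.0, one document gives two answers to a simple operational question: is a tumour biopsy taken between the single nivolumab dose and the first NIVO+ICE? The schema and Section 2.5 say yes. Section 9.1.1 says it is not required.

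What is at stake is mainly patient burden. A research sampling under Section 9.1.2 means three cores beyond those taken for routine or diagnostic use, or fewer where three are not feasible or safe. The schema is a natural quick reference for a site, and a site that relies on it could carry out an invasive procedure that Section 9.1.1 has waived. The exemption is easy to miss, because it sits inside a sentence that does not describe Cohort B patients.

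**Working it through.** The plan states no figure on this point, so there is nothing to reproduce. The check compares each place that bears on a Cohort B biopsy before NIVO+ICE, separately for the two groups of patients that Section 9.1.1 distinguishes.

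| Place | Enrolled before approval of Version 14.0 | Enrolled after approval of Version 14.0 |
|---|---|---|
| Cohort B schema footnote | Required, if safe and accessible | Required, if safe and accessible |
| Section 2.5 | Required in all | Required in all |
| Section 9.1.1 | Not exempted, but no direct Cohort B rule | Exempted |
| Section 10.2 calendar | No on-treatment biopsy | No on-treatment biopsy |
| Section 9.1.3 and Appendix C | No on-treatment label | No on-treatment label |

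**Later enrollees (right column).** The schema footnote and Section 2.5 contradict Section 9.1.1. The calendar, labelling text and form are compatible with the exemption.

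**Earlier enrollees (middle column).** They are outside the exemption, yet the calendar, labelling text and form make no provision for the biopsy that the schema and Section 2.5 ask of them.

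**Placement of the exemption.** The host sentence concerns patients with stable or progressive disease at the first CT/PET who then move to NIVO+ICE. In Cohort B, single-agent nivolumab lasts 2 weeks (Section 5.4.2), and the PET-CT is done at the end of week 8 (Section 10.2, footnote f). Since 2 < 8, a Cohort B patient starts NIVO+ICE before any scheduled response scan. The sentence therefore does not cover Cohort B, and the parenthesis exempts these patients from a rule that was not theirs. Section 9.1.1 has no on-treatment biopsy rule written for Cohort B.

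**Size.** Inputs from Section 12.1.1: at most 35 Cohort B patients, of whom 13 had been treated at the April 2021 expansion.

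- Still to enrol at the expansion: 35 − 13 = 22.
- The 13 count as earlier enrollees, because Version 14 contains the April 2021 update that reports them as already treated.
- How many of the other 22 enrolled after approval is not stated, and neither is the approval date. Section 5.5 implies that some Cohort B patients enrolled before Amendment 14 but gives no count.
- Range under the conflicting instructions: 0 to 22 of 35.

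**The case against.** **The intent can be worked out.** Section 2.5 is background, and its sentence stands above the dated update. Section 9.1.1 is a specific, version-dated exemption, and for later enrollees the calendar, labelling text and form all agree with it. Much of this stands: for those patients, the calendar and form are not further conflicts with Section 9.1.1. But the schema footnote is not background, it is worded as mandatory, and neither it nor Section 2.5 is marked as superseded. A site should not have to infer which of two current instructions governs an invasive procedure.

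**The schema does not require a biopsy in every patient.** This stands. Its requirement depends on safety and access; only Section 2.5 is unconditional.

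**Stronger readings that a reader might infer.** One is that all 22 remaining patients are affected and that only 13 paired samples are left out of 35. The documents do not support this. Twenty-two is the upper end of an unknown count. Thirty-five pairs were never assured, given the schema's qualifier. The comparison in Section 9.3 is also not confined to Cohort B: Cohort A patients not in CR were to be biopsied too, and Section 2.5 reports very few such samples, not none.

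Another is that the conflict makes the trial lose its paired samples. For later enrollees the exemption looks deliberate, so no required sample is lost. For earlier enrollees the biopsy was due before Cycle 2, about two weeks after the first dose. That window would have closed, or nearly so, when Version 14 took effect, so its calendar can hardly have cost them the sample.

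Nor does Section 9.3 need to state an expected number of pairs. It describes its list as anticipated, Section 12.5 calls the correlative work exploratory with no formal testing, and a paired comparison can only use patients with both samples.

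**Limits of the copy.** The schema figure and the consent form are not in the public text. What patients were told about the biopsy, and where the footnote mark sits in the figure, cannot be checked.

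**Conclusion.** The point holds as an internal contradiction with a practical consequence. Within Version 14, the Cohort B schema footnote and Section 2.5 call for a biopsy before NIVO+ICE without a version exception, while Section 9.1.1 exempts later enrollees. The remaining collection documents have no on-treatment time point for any Cohort B patient.

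The contradiction itself does not depend on a count. Its reach is 0 to 22 of 35 patients, assuming that the 13 treated at the April 2021 expansion all enrolled before Version 14.0 was approved. The harm at issue is an avoidable research biopsy. The primary endpoints, sample sizes and two-stage rules are untouched, and the related analyses are exploratory. It should be corrected, because it can change what is done to patients and the correction is cheap. Which biopsy rule is right is not for this review to say.

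**What to change.** Reconcile six places so that all state one on-treatment biopsy requirement for Cohort B, by protocol version:

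1. the Cohort B schema footnote;
2. Section 2.5;
3. Section 9.1.1, with a direct Cohort B rule of its own in place of a parenthesis in the Cohort A sentence;
4. the Cohort B calendar in Section 10.2, including its footnotes;
5. the labelling text in Section 9.1.3;
6. the time-point boxes on the tissue form in Appendix C. If the biopsy applies to any Cohort B patients, items 5 and 6 need an on-treatment option.

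The cost is amendment wording and a revised form. Neither the sample size nor the analysis plan changes.

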3.1 Inclusion Criteria

- Patients must have histologically documented or cytologically confirmed Hodgkin lymphoma; confirmation must include CD30 expression.

- Patients must be either refractory to or relapsed after only induction therapy. Patients who do not achieve CR after induction therapy are considered primary refractory and are allowed to enter study.
- Age \geq 18 years old and > 40 kg
- Patients must have ANC $\geq 1500/\mu\text{L}$, Plt $\geq 75,000/\mu\text{L}$, and hemoglobin ≥ 8.5 g/dl. Filgrastim can be given before and during treatment to achieve target ANC $\geq 1500 \mu\text{L}$. Platelet transfusion and packed red blood cell transfusion can also be given prior to the start of treatment and during treatment to achieve a target plt $\geq 75,000/\mu\text{L}$ and hemoglobin of ≥ 8.5 g/dl, provided that patients have not received growth factors for at least 14 days prior to entering trial.
- Patients must have measurable disease > 1.5 cm evidenced by CT scan of the neck/chest/abdomen/pelvis or CT/PET scans.
- Life expectancy of greater than 3 months.
- ECOG of 0-2.
- Documented informed consent of the participant or legally responsible guardian.

Patients must have normal organ and marrow function as defined below:

- DLCO $\geq 60\%$
- Total bilirubin within 1.5x the upper limit of normal (ULN) institutional limits. Patients with elevation of unconjugated bilirubin alone, as in Gilbert's disease, are eligible.
- AST/ALT ≤ 3.0 x the institutional upper limit of normal (unless demonstrated Hodgkin lymphoma involvement of the liver). Estimated creatinine clearance ≥ 30 ml/min (Cockcroft-Gault) and/or 24 urine analysis as needed
- For patients with HL involvement of the liver, AST/ALT ≤ 5.0 x institutional ULN. Total bilirubin within 3.0 x institutional ULN. (Although patients with HL involvement of the liver are frequently excluded from trials, their liver function tests often improve after treatment. The studies that led to nivolumab approval did not reveal any increased signals of liver toxicities attributed to nivolumab.)
- PT/INR < 1.5 x ULN and PTT (aPTT) < 1.5 x ULN.

